
KEY PERSONNEL (List names of all investigators including PI and their respective specialties)

Name	Professional Discipline/ Specialty	Role in the Project
1. [name]	Assistant Scientist / Immunology	Principal Investigator
2. [name]	Head, CHP/ Epidemiology	Co- Principal Investigator
3. [name]	Head, MHRP/ Epidemiology	Co-investigator
4. [name]	Associate Scientist / Epidemiology	Co-investigator
5. [name]	Senior Scientist / Immunology	Co-investigator
6. [name]	Division Director, CSD/ Nutrition	Co-investigator

DESCRIPTION OF THE RESEARCH PROJECT

Hypothesis to be tested:

Concisely list in order, in the space provided, the hypothesis to be tested and the Specific Aims of the proposed study. Provide the scientific basis of the hypothesis, critically examining the observations leading to the formulation of the hypothesis.

A. Long term supplementation of iron and/or zinc or micronutrient mix in infants six months onward will:

1. increase the levels of total IgA levels in serum (in infants who will receive zinc alone) and s-IgA in stool (in infants who will receive zinc alone or iron alone or in combination)
2. increase specific IgG response against vaccines (measles or oral polio vaccine) (in infants who will receive zinc alone or iron alone or in combination)
3. improve cellular immune status by enhancing the proliferative response against mitogen (PHA) and response against multiple antigens (in infants who will receive zinc alone or iron alone or in combination)
4. enhance the numbers of Pan T cells (CD3), T helper cells (CD4) (in infants who will receive zinc alone) and natural killer cells (CD56 / CD16) (in infants who will receive iron alone) in systemic circulation
5. activate complement components in blood (in infants who will receive zinc alone)

B. Infants who will receive the micronutrient mix will have an overall positive effect on the immune status as described above.

Specific Aims:

Describe the specific aims of the proposed study. State the specific parameters, biological functions/ rates/ processes that will be assessed by specific methods (TYPE WITHIN LIMITS).

To study the following before and 6 months after supplementation:

1. The levels of total and specific IgA (response against measles/oral Polio vaccine) in serum and secretory IgA in stool.
2. To study the proliferative responses of lymphocytes to mitogens and to measure IL-2 levels in the culture supernatant.

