3. Multitest CMI skin test will be performed to study the cell-mediated immune response in infants.

4. To study phenotypic changes in the peripheral blood mononuclear cells.
5. To study the complement response (C3, C5) in infants.

Background of the Project including Preliminary Observations

Describe the relevant background of the proposed study. Discuss the previous related works on the subject by citing specific references. Describe logically how the present hypothesis is supported by the relevant background observations including any preliminary results that may be available. Critically analyze available knowledge in the field of the proposed study and discuss the questions and gaps in the knowledge that need to be fulfilled to achieve the proposed goals. Provide scientific validity of the hypothesis on the basis of background information. If there is no sufficient information on the subject, indicate the need to develop new knowledge. Also include the **significance and rationale** of the proposed work by specifically discussing how these accomplishments will bring benefit to human health in relation to biomedical, social, and environmental perspectives. (DO NOT EXCEED 5 PAGES, USE CONTINUATION SHEETS).

Original protocol:

The above study (entitled "A community-based, randomized, controlled trial to assess the efficacy of iron and / or zinc or a micronutrient mix supplementation to reduce anemia and morbidity and to improve growth and development in Bangladeshi infants") (Protocol #99-014) is a community based, double blind, randomized, controlled trial to evaluate the efficacy of weekly supplementation of iron and / or zinc or a micronutrient mix for six months in infants beginning 6 months of age. Five groups will be studied. (i) 20 mg iron with 1 mg riboflavin, (ii) 20 mg zinc with 1 mg riboflavin, (iii) both iron and zinc with riboflavin, (iv) a micronutrient mix (UNICEF mix), and (v) riboflavin only (placebo) will be studied.

The outcome variables that will be measured are: (a) iron status, (b) zinc status, (c) copper status, (iv) diarrheal morbidity, (v) growth, and (f) cognitive, psychomotor and behavioural development. Eight hundred infants will be selected from the Matlab villages and will be enrolled in the study over a period of six months. Selection criteria are described in the original

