proposal. Infants will be stratified by height-for-age z-scores using -2 z-score height-for-age as the cut-off. The infants in each strata will then be randomized to one of the 5 study groups using a block randomization procedure. Trained community health workers (CHW) will visit the infants every week to feed the infants with the assigned supplements as well as collect morbidity data. Growth, weight, length, and MUAC of the infants will be measured at enrollment and thereafter every two months. Finger prick blood samples will be collected from each study infant at the start and end of the follow-up for hemoglobin test. About 3 ml of venous blood samples will be collected by a trained nurse from 50% of the study infants at the start and the end of the follow-up (6 months and 12 months) and will be tested for serum transferrin receptor (sTfR), zinc and copper. An assessment of mental, psychomotor and behavioural developments will be carried out in a 50% sample of study infants at 6 months and 12 months by a trained psychologist using Bailey" Scale of Infant Development, Version 2.

Addendum.

Micronutrients, the immune system and resistance to infection form an absolute trinity. One influences the other. The severity of the immunological impairment depends on the extent and nature of the nutritional status, the presence of infections and the age of the individual (1). Infection by itself results in micronutrient losses and often produces immunosuppression. In recent years greater attention has been devoted to the possible effects of individual nutrients on risk of infection.

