hypothesis that supplementation with zinc, vitamin A or both can improve vibriocidal as well as antigen specific antibody response to killed 01 Cholera vaccine. Development of the immune system can be assessed by testing the antibody response to immunizations with measles vaccine that is given at the age of 9 months. Till date, there is no report on the effect of zinc supplementation on antibody response to measles vaccination. There are studies that indicate that simultaneous administration of measles vaccine and vitamin A supplements had either no negative effect on measles immunity or a significant positive effect (30, 31). On the other hand, reports of simultaneous vitamin A supplementation interfering seroconversion to live measles vaccine in infants is also present (32). There is evidence that infant formula fortified with nucleotides can significantly enhance concentration of antibody against *Haemophilus influenzae* type b and diphtheria during infancy (33) suggesting that dietary factors play a significant role in the antibody responses of infants to immunization.

Research Design and Methods

Describe in detail the methods and procedures that will be used to accomplish the objectives and specific aims of the project. Discuss the alternative methods that are available and justify the use of the method proposed in the study. Justify the scientific validity of the methodological approach (biomedical, social, or environmental) as an investigation tool to achieve the specific aims. Discuss the limitations and difficulties of the proposed procedures and sufficiently justify the use of them. Discuss the ethical issues related to biomedical and social research for employing special procedures, such as invasive procedures in sick children, use of isotopes or any other hazardous materials, or social questionnaires relating to individual privacy. Point out safety procedures to be observed for protection of individuals during any situations or materials that may be injurious to human health. The methodology section should be sufficiently descriptive to allow the reviewers to make valid and unambiguous assessment of the project. (DO NOT EXCEED TEN PAGES, USE CONTINUATION SHEETS).

Study Subjects

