Infants from selected Matlab villages meeting the inclusion and exclusion criteria as given in the original protocol will be enrolled in the parent study. In addition to the criteria set for the original protocol, subjects who develop any infection including ARI or diarrheal diseases will be excluded from the proposed study since the infection may have an effect on the immune responses of these subjects.

Outcome Variables and Sample size Determinants

The following outcome variables will be measured:

- | | | |
|------|-------------------------|---|
| (i) | Humoral responses: | IgA in serum
Serum IgG responses to measles/Polio vaccines
sIgA in stool

Complement components C3 and C5 in serum |
| (ii) | Cell mediated immunity: | Proliferative response of peripheral lymphocytes to mitogens
Interleukin 2 in culture supernatant of proliferative lymphocytes
Phenotypic changes in the peripheral blood |

Table 1. Sample size calculations:

Outcome variables	Expected levels in the control group	Expected level in the treatment group (expected % improvement/reduction)	*Sample size required in each group	References
1. IgA in serum, mg/L	81±32	111±26	19	17
2. s-IgA in stool, g/L (for zinc)	0.05±0.01	1.1±0.45	3	36
3. s-IgA in stool, mg/dl (for iron)	0.05±0.01	7.4±0.25	2	27
4. Antibody titers against Polio virus vaccine	169	346	99	33
5. [§] Response to PHA	31±9	58±13	4	17
6. IL-2 in culture supernatant, units/ml	106.5±99	137.3±67	149	28
7. CMI, % of anergic children	67%	47%	131	15
8. Phenotypic changes	0.43±0.53	2.09±1.68	12	28
a) CD3				
b) CD4	0.30±0.39	1.43±1.24	14	28
c) CD8	0.13±0.17	0.76±0.54	9	28

[§]Stimulation index, mean±SD. A loss of follow-up of 20% has been included. *Sample size required in each group of infants supplemented with either zinc alone or iron alone, or zinc and iron in combination or the multimix. Allowance for 10% drop-out has been made. Since sample size is different for each variable, for convenience we decided that for variables 1, 2, 3, 5, and 8, sample size is 20. Sample size for variables 4, 6 and 7 will remain the same as shown in the table.

Methodology

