In the original project, blood (3 ml) samples will be collected before micronutrient supplementation and 6 months later. In the present proposal, additional 1ml of blood will be collected at the same time points, therefore the total blood volume will be 4 ml. Mononuclear cells will be separated from total blood and used for various purposes. Stool samples will be collected at the time of blood collections.

Blood:

Lymphocytes

Blood (4 ml) will be collected in heparinized tubes. Lymphocytes separated from venous blood upon Ficoll-Hypaque separation will be used for proliferation response to mitogens (PHA) and for phenotyping of lymphocytes by flow cytometry. Lymphocytes will be frozen and carried in

liquid nitrogen to the Karolinska Institutet at the Division of Infectious Diseases, Huddinge University Hospital where phenotyping will be performed.

Plasma

Total IgA contents will be determined in plasma using ELISA with pooled human Swedish milk with a known IgA concentration of 1 mg/ml as a standard (34). In brief, Nunc plates will be coated with affinity pure goat antihuman IgG as a concentration of 1 µg/ml in PBS(phosphate buffered saline) (100 µl/well).and incubate the overnight at room temperature. Plates will be washed 2 times with PBS and blocked with 1% BSA-PBS (bovine serum albumin-phosphate buffered saline) (200 µl/ml) and will be incubated for 30 min at 37°C. After incubation, plates will be washed 3 times with PBS-Tween and once with PBS. Standard Swedish milk (2 µg/ml) and samples (100 µl/well) will be added to the specific wells. In case of samples initial dilution will be 1: 500 and then 3 fold serial dilution continued. . Plates will be incubated for 90 minutes at room temperature. After washing as above, conjugate Goat anti human-IgA-HRP (horse radish peroxidase) (1:4000 in 0.1% BSA-PBS-Tween, 100 µl/well) will be added and incubated for 1 hrs in room temperature. After washing 3 times, OPD substrate will be added and plates will be read after 20 minutes of development at 450nm.

Antibody titers to measles immunization will be carried out using ELISA (31). Complement C3 and C5 in plasma will be measured using commercially available kits (Amersham Pharmacia Biotech, England). IL-2 will be measured in the culture supernatant from mitogen-stimulated cells after proliferation using commercially available kits (R&D Systems, Minneapolis, USA).

Stool

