Immunological assays including enzyme linked immunosorbant assays (ELISA), lymphocyte proliferation assay, will be carried out at ICDDR,B since the techniques have been standardized and the equipment needed for carrying out the assays are available in ICDDR,B. However, to perform sterile work, a biohazard hood will be required at Matlab. For separating lymphocytes from blood, a refrigerated table-top-centrifuge will also be needed at Matlab. An ultra low freezer (-80° C) will be required to store lymphocytes after separation from whole blood. These lymphocytes will be phenotyped later by flow cytometry. Since fluorescent associated cell sorter (FACS) is not available at ICDDR,B, frozen cells have to be carried in dry ice (-70° C) to Sweden. FACS will be available to the PI to perform flow cytometric assay (phenotyping) at the Division of Infectious Diseases, Karolinska Institutet, Sweden.

Data Analysis

Describe plans for data analysis. Indicate whether data will be analyzed by the investigators themselves or by other professionals. Specify what statistical softwares packages will be used and if the study is blinded, when the code will be opened. For clinical trials, indicate if interim data analysis will be required to monitor further progress of the study. (TYPE WITHIN THE PROVIDED SPACE).

Baseline characteristics of the different supplementation/treatment and comparison groups will be examined for group comparability as described in the original protocol.

To examine the effect of individual micronutrient i.e. zinc or iron on the immune parameters between the pre and post supplementation days, Wilcoxon-signed Rank test will be used. To examine the proportion of subjects responding to a particular supplement, Chi-square test will be performed. To examine the potential additive and multiplicative effects of providing zinc, iron and other micronutrients on the immune parameters, multiple regression analyses will be performed.

Ethical Assurance for Protection of Human Rights

Describe in the space provided the justifications for conducting this research in human subjects. If the study needs observations on sick individuals, provide sufficient reasons for using them. Indicate how subject's rights are protected and if there is any benefit or risk to each subject of the study.

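### The effect of zinc or iron alone is tested pre/post within one arm, without the riboflavin-only control, although measles vaccination falls between the two samples

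*Protocol*

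**What the plan says.** The Data Analysis section of the protocol names three analyses.

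- For the effect of a single supplement, it refers to an "individual micronutrient i.e. zinc or iron on the immune parameters between the pre and post supplementation days, Wilcoxon-signed Rank test will be used".
- For the proportion of infants responding to a supplement, it names a chi-square test, with no comparison group.
- For additive and multiplicative effects of zinc, iron and other micronutrients, it names multiple regression. The abstract for the ethical review committee codes the corresponding parent-trial regression by zinc or no zinc and iron or no iron.

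Other sections bear on the first analysis:

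- **Control arm.** The fifth randomised group is the control: "riboflavin only (placebo) will be studied" (Original protocol).
- **Sampling.** The parent trial draws venous blood "from 50% of the study infants at the start and the end of the follow-up (6 months and 12 months" of age). Under Methodology, "samples will be collected before micronutrient supplementation and 6 months later", and the addendum's extra blood is taken at those same times.
- **Vaccination.** The Addendum background proposes to assess immune development by the "antibody response to immunizations with measles vaccine that is given at the age of 9 months".
- **Hypothesis A2.** Supplementation will "increase specific IgG response against vaccines (measles or oral polio vaccine").
- **Sample size.** One column of Table 1 is headed "Expected levels in the control group", and the next gives the expected level in the treatment group.

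**The concern.** A signed-rank test of post against pre in the zinc arm asks whether the level changed in those infants. It does not ask whether zinc changed it. Anything that moves the level in all arms between the two samples is credited to the supplement.

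For measles IgG such a cause is certain to be present, because the vaccine is given midway between the samples. Hypothesis A2 concerns a larger vaccine response, and a significant rise in a vaccinated arm is no evidence for that. For the other quantitative measures the common cause would be age: the Addendum background itself lists age among the determinants of immune impairment. Polio IgG is also exposed, but the protocol gives no polio vaccination dates, so the direction cannot be stated.

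The protocol says that a positive result might lead to public-health use of supplements to make vaccines work better. A within-arm vaccine response would be false support for that step.

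**Working it through.** **1. Which comparison the trial was sized for.** Table 1 can be reproduced as a comparison of two independent groups, assuming two-sided 5% and 80% power (neither is stated) and the 20% loss in its footnote:

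n = 2 × (1.96 + 0.84)² × (s₁² + s₂²)/2 ÷ d², then n/0.8.

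- Serum IgA: (32² + 26²)/2 = 850 and d = 30, so n = 2 × 7.85 × 850/900 = 14.8, rounded up to 15; 15/0.8 gives 19 (stated 19).
- IL-2: (99² + 67²)/2 = 7145 and d = 30.8, so n = 118.2, rounded up to 119; 119/0.8 gives 149 (stated 149).
- Anergy, 67% against 47%, continuity-corrected: 105/0.8 gives 132 (stated 131).

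The other rows with SDs also agree. The polio titre row has no SD and cannot be checked. The sizing therefore rests on a between-arm contrast that the signed-rank test does not make.

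**2. Infants per arm.** 800 × 50% ÷ 5 = 80. Losses of 10% and 20% leave 72 and 64. Table 1 asks for 99 for antibody titre.

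**3. Measles IgG with no supplement effect.** Assumptions, none from the protocol: 90% seroconvert; log10 rise in seroconverters 0.5 or 1.0 (SD 0.5); change in the others 0 or −0.3 (SD 0.2); the same in both arms.

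By hand, for rise 0.5 and others 0:
- mean change = 0.9 × 0.5 = 0.45
- variance = 0.9 × 0.25 + 0.1 × 0.04 + 0.9 × 0.1 × 0.5² = 0.2515, so SD = 0.50
- at n = 64 the standard error is 0.50/8 = 0.063, so the mean rise is about 7 standard errors.

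Simulation (4,000 runs per cell, two-sided 5%, n = 64, 72, 80 and 99, 16 cells):

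| Test | Significant |
|---|---|
| Signed-rank rise, supplemented arm | 100% |
| Signed-rank rise, riboflavin-only arm | 100% |
| Rank-sum on change, between arms | 4.2–5.5% |

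In a five-arm regression on change (zinc, iron, zinc × iron, mix; 2,000 runs; rise 0.5, others 0), the zinc term is significant in 5.1% at n = 64 and 5.6% at n = 80. The zinc-arm signed-rank test is significant while the zinc term is not in 95.0% and 94.5% of trials.

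**4. Measles IgG if a supplement halved the rise (0.25 against 0.5, others 0).**

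| n per arm | Signed-rank shows a significant rise | Rank-sum shows the arm below riboflavin-only |
|---|---|---|
| 64 | 94.7% | 68.8% |
| 80 | 97.8% | 78.3% |
| 99 | 99.3% | 87.7% |

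**5. Other quantitative measures.** Assumed common age drift in SD units of change, no supplement effect. Share of trials with a significant signed-rank rise:

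| n per arm | 0.2 SD | 0.3 SD | 0.5 SD |
|---|---|---|---|
| 20 (stated for variables 1, 2, 3, 5 and 8) | 12.8% | 24.0% | 53.5% |
| 64 | 33.3% | 62.6% | 97.1% |
| 80 | 39.5% | 73.9% | 98.8% |

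The between-arm rank-sum test is significant in 4.3–5.2% throughout.

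**The case against.** The strongest reply is that the right comparison is already planned. With five arms and terms for zinc, iron, their interaction and the mix, the zinc coefficient on change is exactly zinc-only minus riboflavin-only. That is true, so the plan as a whole does not lack a between-arm analysis. But Data Analysis assigns the regression to joint effects and the single-supplement effect to the signed-rank test. The order of analyses may well be left to a SAP, but this assignment is stated text and points to the wrong test.

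The chi-square test is no rescue: it names no comparator and does not test levels.

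Some criticism of the figures stands. The vaccine-response inputs are assumed, and once most infants are taken to respond, 100% significance follows almost automatically. The disagreement with the regression is then little more than 100% minus the 5% error rate. The halved-rise case has no basis in the protocol for zinc or iron; it only illustrates what the test would miss. The figures at 99 per arm exceed the roughly 80 infants available. Beyond measles IgG, the protocol gives neither the size nor the direction of any age drift.

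It is also fair that the Table 1 footnote applies its sizes to the supplemented groups and does not list riboflavin-only. The control column and the mention of comparison groups in Data Analysis imply that controls are assayed, but the addendum does not say so outright.

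**Conclusion.** The concern holds: the test named for the single-supplement effect is wrong as written. For measles IgG the argument needs only the sampling ages, the vaccination age and a vaccine that works in most infants. That IgG rises in every arm is an inference from this timing; the protocol does not state it. At the attainable 64 to 80 infants per arm and under the stated assumptions, the test finds an effect in 100% of trials when there is none, against 4 to 6% for the between-arm comparison. It would still show a significant rise in about 95 to 98% of trials if a supplement halved the response.

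For the other quantitative measures the flaw is the same in kind, but its size is unknown. With an assumed drift of 0.2 to 0.5 SD, the false-positive rate runs from 13 to 53% at n = 20 and from 33 to 99% at n = 64 to 80.

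**What to change.** In Data Analysis, state that the pre/post signed-rank test is descriptive only. For measles and polio IgG and the other quantitative immune measures, test each supplemented arm (zinc, iron, both, mix) against riboflavin-only. Use either a rank-sum test on change from baseline or the 12-month value adjusted for baseline; fix one of the two in advance, and report the difference with a 95% CI. Keep the regression for additive and multiplicative effects. State explicitly that the assays are run in the riboflavin-only arm.

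The change is one of wording. It needs no new visits or staff, and no new samples provided the riboflavin-only infants are assayed as Table 1 implies. The price is precision, and there are four comparisons per measure, for which the protocol should say how multiplicity is handled.

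- **Half-width of the 95% CI** for a difference in mean change, t × √(2/n) in SD units: 2.02 × 0.316 = 0.64 at n = 20; 1.98 × 0.177 = 0.35 at n = 64; 1.98 × 0.158 = 0.31 at n = 80.
- **Measles IgG**, with the assumed SD of change of 0.50 to 0.62 log10: a 1.50- to 1.64-fold titre ratio at n = 64 and 1.43- to 1.56-fold at n = 80.
- **Power for about a two-fold titre difference**, the polio ratio in Table 1 (log10(346/169) = 0.311), over the same SDs: 81–94% at n = 64 and 89–97% at n = 80, but 61–78% if the infection exclusions left 40 per arm (an assumed figure).
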